Score	Action/ Movement	Initial valoration	Intermedia valoration	Final valoration
Sitting patient 0: no movement 9: palpable contraction 14: perform movement but not full range vs gravity 19: full range of motion vs gravity but not vs resistance 25: movement vs resistance but less than contralateral 33: normal strength	1. Shoulder abduction 2. Elbow flexion Voluntary movement of 90°			
0: no movement 11: prehension starts 19: takes the cube but is not able to hold it vs gravity 22: he takes the cube and is able to hold it vs gravity but not vs resistance 26: take the cube overcomes gravity and resistance but is less than the contralateral 33: regular clamp	3. Grasp Hand: 2.5 cm cube between thumb and other fingers.			
0: no movement 9: palpable contraction 14: perform movement but not full range vs gravity 19: full range of motion vs gravity but not vs resistance 25: movement vs resistance but less than contralateral 33: normal strength	4. Hip flexion 5. Knee extension 6. Ankle dorsiflexion			
Upper limb Index: $1+2+3+(1)/100$				
Lower limb index: $4+5+6+(1)/100$				
Total motor index: (Motor Index of UL + Motor Index of LL/2)/100				

Indicators. The application process is described in the procedures section. They will always be performed by the same doctor, who will ignore which therapy group the patient corresponds to, at the beginning, at 6 and 12 treatment sessions.

The equivalence of the results for the Motor Index is considered based on 100 total points (sum of upper limb + lower limb divided by 2).

Qualification	Equivalence
- 100 a 90 points.	Independent patients with rehabilitation for work adjustment and activities of daily living.
- 89 a 80 points.	Independent patients with limitations, who need integral rehabilitation treatment.
- 79 a 70 points.	Semi-dependent patient who needs external help and orthotics.
- 69 a 60 points.	Patients with help-dependent limitation.
- Less 60 points.	Dependent patient needs prolonged rehabilitation.

The equivalence of the results for the Fugl-Meyer scale is considered based on 100 total points, taking into account only the motor aspect of the lower and upper limb (maximum of 66 points for the upper limb + 34 points for the lower limb). The original equivalence established by the author in 1980 and the most recent one proposed by other authors are shown.

Fugl-Meyer (1980)	Duncan, Goldstein, Horner, Landsman, Samsa y Matchar (1994)
<50 = Severo	0-35 = Muy severo
50-84 = Marcado	36-55 = Severo

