	80. Extension				81. Extension			
Forearm	82. Pronation				83. Pronation			
	84. Supination				85. Supination			
Wrist	86. Flexion				87. Flexion			
	88. Extension				89. Extension			
Fingers	90. Flexion				91. Flexion			
	92. Extension				93. Extension			
Hip	94. Flexion				95. Flexion			
	96. Abduction				97. Abduction			
	98. External rotation				99. External rotation			
	100. Internal rotation				101. Internal rotation			
Knee	102. Flexion				103. Flexion			
	104. Extension				105. Extension			
Ankle	106. Dorsiflexion				107. Dorsiflexion			
	108. Plantar flexion				109. Plantar flexion			
Foot	110. Eversion				111. Eversion			
	112. Inversion				113. Inversion			
	Sum of points							
	Partial score	#	/ 44	points				
	TOTAL score	#	/226					

Ini. Val.: initial valoration; Interm. Val.: intermediate valoration; Fin. Val.: final valoration.

The assessments will be made before starting the therapy (Initial value), at 6 sessions and at the end of therapy (12 sessions).

b) **Motor index scale.** It is a method of scoring muscle strength on the hemiplegic side by assessing the action of six key muscles, in a sitting or lying position. It is examined: shoulder abduction and elbow flexion (upper limb), grasp (hand), hip flexion, dorsiflexion and ankle knee extension. The maximum score in the upper limb is 100 and in the lower limb 100. The global motor index score is obtained by adding the position obtained in the upper limb with the lower limb and dividing by two (Annex 2. Motor evaluation of plegic limbs /paretic).

Score	Action/ Movement	Initial valoration	Intermedia valoration	Final valoration
Sitting patient 0: no movement 9: palpable contraction 14: perform movement but not full range vs gravity 19: full range of motion vs gravity but not vs resistance 25: movement vs resistance but less than contralateral 33: normal strength	1. Shoulder abduction			
	2. Elbow flexion Voluntary movement of 90°			
0: no movement 11: prehension starts 19: takes the cube but is not able to hold it vs gravity 22: he takes the cube and is able to hold it vs gravity but not vs resistance 26: take the cube overcomes gravity and resistance but is less than the contralateral 33: regular clamp	3. Grasp Hand: 2.5 cm cube between thumb and other fingers.			

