0: no movement 11: prehension starts 19: takes the cube but is not able to hold it vs gravity 22: he takes the cube and is able to hold it vs gravity but not vs resistance 26: take the cube overcomes gravity and resistance but is less than the contralateral 33: regular clamp	Grasp Hand: 2.5 cm cube between thumb and other fingers									
0: no movement 9: palpable contraction 14: perform movement but not full range vs gravity 19: full range of motion vs gravity but not vs resistance 25: movement vs resistance but less than contralateral 33: normal strength	Hip flexion									
	Knee extension									
	Ankle dorsiflexion									
Upper limb Index: $1+2+3+(1)/100$										
Lower limb index: $4+5+6+(1)/100$										
Total motor index: $(\text{Motor Index of UL} + \text{Motor Index of LL})/2/100$										

Ini. Val.: initial valoration; Interm. Val.: intermediate valoration; Fin. Val.: final valoration

Fine clamp quality test (Spanish version)

Score	Action/ Movement	Reality Virtual			Restriction and Induction of Movement			TF and TO habitual		
		Ini. Val.	Interm. Val.	Fin. Val.	Ini. Val.	Interm. Val.	Fin. Val.	Ini. Val.	Interm. Val.	Fin. Val.
0: inability to take the cube 1: Grab with your whole hand 2: Radial or tridigital clamp 3: Forefinger thumb clamp	1.4 cm 2									
	2.5 cm 2									
	3.1 cm 2									

Ini. Val.: initial valoration; Interm. Val.: intermediate valoration; Fin. Val.: final valoration.

LANGUAGE EVALUATION

Boston aphasia intensity scale (Spanish version)

Description of language features	Score	Reality Virtual			Restriction and Induction of Movement			TF and TO habitual		
		Ini. Val.	Interm. Val.	Fin. Val.	Ini. Val.	Interm. Val.	Fin. Val.	Ini. Val.	Interm. Val.	Fin. Val.
Absence of speech or listening comprehension	0									
Communication is made entirely from incomplete expressions. It requires inference, questions and guessing by the listener. The flow of information can be exchanged, it is limited and the weight of the conversation falls on the listener.	1									
The patient can, with the help of the examiner, have a conversation on familiar topics. There is frequent failure to express an idea, but the patient shares the weight of the conversation with the examiner.	2									
The patient can deal with virtually all problems of daily living, with little or no help. However, reduced speech and/or comprehension make conversation on certain types of topics extremely difficult or impossible.	3									

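### The total Motor Index line in two scoring tables halves only the lower limb, against the mean of the two limbs given in the protocol's own text and in Annex 2

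*Combined protocol and SAP*

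**What the plan says.** The Motor Index scores six actions, three in the upper limb (UL) and three in the lower (LL), at the initial, intermediate and final assessments. The scoring table appears under Variables (motor function of the thoracic and pelvic limbs) and again under Procedures 2 b). Both print the total as "Total motor index: (Motor Index of UL + Motor Index of LL/2)/100".

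The text next to each table says something else:

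- Variables, just below the table: "The equivalence of the results for the Motor Index is considered based on 100 total points (sum of upper limb + lower limb divided by 2".
- Procedures 2 b), just above the table: "The global motor index score is obtained by adding the position obtained in the upper limb with the lower limb and dividing by two". The same paragraph sets the limb limits: "The maximum score in the upper limb is 100 and in the lower limb 100".

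The Annex 2 Motor Index form puts the bracket around the sum of the two limbs before halving, in agreement with the text. The Variables section then sorts totals into dependence classes with lower limits of 90, 80, 70 and 60 points, and a top of 100.

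**The concern.** The table line and the text are two different scoring rules for a named outcome scale. The text rule is a plain mean of the limbs. The table line adds the whole upper-limb index to half of the lower-limb index. That changes the level of every total and the relative weight of the limbs, and it lets scores run past the top of the stated scale. Anyone deriving totals from the table would get values that do not fit the dependence classes. Changes in the total would also be larger than under the text rule, by half of the upper-limb change.

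**Working it through.** **Inputs**

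- Each of the six items has a maximum of 33 (Motor Index table).
- Limb index: the three item scores plus 1, followed by /100 (same table).
- Limb maximum: 100 for each limb (Procedures 2 b).
- Dependence classes: below 60, 60–69, 70–79, 80–89, 90–100 (Variables).
- Example UL value: Table 1, virtual-reality group at the initial assessment, hand 20.77 + shoulder-elbow 41.15 = 61.92. Table 1 labels this sum as a total motor index, but it contains no leg items, so it is used here as an upper-limb value.
- Example LL value: the documents give none. I assume 40, 60 and 80.

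**Step 1. Reproduce the stated limb maximum.** 33 + 33 + 33 + 1 = 100, as stated. This works only if /100 means out of 100.

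**Step 2. Maximum of the total.**

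- Text and Annex 2: (100 + 100)/2 = 100, which matches the 100-point scale and the top class.
- Table line: 100 + 100/2 = 150, which does not.
- If /100 is taken as division in both totals, the maxima are 1.5 and 1.0. The ratio is the same, and the point classes can no longer be used.

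**Step 3. Gap between the rules.** (UL + LL/2) − (UL + LL)/2 = UL/2, whatever LL is. A limb index runs from 1 (all items 0) to 100, so the excess runs from 0.5 to 50 points.

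**Step 4. Weights.** UL and LL enter the table line as 1 to 1/2, so the upper limb counts twice as much. UL 80 with LL 40 gives 80 + 20 = 100, and UL 40 with LL 80 gives 40 + 40 = 80. The mean is 60 in both cases.

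**Step 5. Example with UL = 61.92.**

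| Assumed LL | Table line, UL + LL/2 | Class | Text rule, (UL + LL)/2 | Class |
|---|---|---|---|---|
| 40 | 61.92 + 20 = 81.92 | 80–89 | 101.92/2 = 50.96 | below 60 |
| 60 | 61.92 + 30 = 91.92 | 90–100 | 121.92/2 = 60.96 | 60–69 |
| 80 | 61.92 + 40 = 101.92 | off the scale | 141.92/2 = 70.96 | 70–79 |

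The excess is 61.92/2 = 30.96 in each row. If the added 1 is missing from the pilot sum, UL is 62.92 and the excess is 31.46.

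**Step 6. Does the class always change?** No. UL 30 with LL 40 gives 30 + 20 = 50 against 35, both below 60. Over all 6^6 = 46,656 combinations of item scores, equally weighted, about 81% change class (counting scores above 100 as outside the classes) and about 15% exceed 100. This shows the reach of the formula and is not a distribution of patients.

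**The case against.** The best reply is that the documents already resolve the matter. The intended rule stands beside both faulty lines. Procedures item 4 has results noted on Annexes 2 and 4, and the Annex 2 form carries the mean. The notation in these tables is also loose: taken strictly, the limb lines would add 0.01 rather than 1. Read just as loosely, the total line could be meant as the two limbs added, halved, out of 100. This stands as an account of intent, and it makes a misplaced bracket the likely explanation. It does not make the line correct: the same wrong bracket is printed twice, and the data-handling and analysis sections give no derivation rule that would override it. The bracket in Annex 2 should be checked against the printed form, but the contradiction holds on the two text statements alone.

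A reader might infer that totals will not be comparable between visits. The documents do not support that. One doctor performs all the assessments, and one Annex 2 sheet holds the three visits side by side. Even the wrong rule, used throughout, would keep visits and groups on one scale, though with the wrong weights.

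A reader might also infer that every patient would land in a different dependence class. Step 6 shows otherwise.

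**Conclusion.** The total line in both tables is wrong as written, by the protocol's own text and its own 100-point limit. If it were used, the maximum would be 150 instead of 100, the upper limb would have double weight, and each total would be too high by UL/2, about 31 points at the pilot value. The figure of 150 rests on reading /100 as out of 100, which the stated limb maximum supports. The totals in the example also rest on the assumed LL values, but the 31-point gap does not.

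The consequence is limited. It would be tempting to conclude that the main comparison or the sample size is compromised, but the documents do not support this. The working hypothesis and the sample size rest on the Fugl-Meyer scale, the separate limb indices do not use the faulty line, and the statistical section plans no analysis of dependence classes. Nor do the documents show that any total has been or will be computed from the table line. This is a minor correction to an outcome's scoring rule.

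**What to change.** In both tables (Variables and Procedures 2 b), print the total as (UL + LL)/2, the rule that the text and Annex 2 already state. Add a note to the Motor Index tables and the Annex 2 form that /100 means out of 100, so that it is not taken as a division in the limb lines or the total. The cost is two corrected table lines and a short note, with no change to assessments, sample size or analysis. If totals have already been derived, confirm which rule was used. They can be recalculated from the six recorded item scores.

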What is the effect of different therapeutic modalities supported by Virtual Reality or Restriction and Induction of Movement compared with usual Physical and Occupational Therapy on motor recovery of paretic limbs in patients with Cerebrovascular Event?

Secondary questions

1. To determine the relationship between the therapeutic management group and motor evolution with changes in language (aphasy).
2. To measure the level of patient satisfaction with the treatment received.
3. To relate the level of patient satisfaction with adherence to treatment.

WORK HYPOTHESIS

A therapeutic program supported in virtual reality will increase the motor function of the paretic thoracic extremity of patients with CVE by at least 38.6** average points measured with the Fugl-Meyer scale compared with usual physical and occupational therapy.

**The smallest difference in the improvement of the hemiparesis function calculated in points with the Fugl Meyer scale, found in patients with characteristics similar to those of the patients in this protocol, was taken. As well as the lowest standard deviation to cover all values^{46, 47}.

AIM

To measure the effect of different therapeutic modalities supported by Virtual Reality or Restriction and Induction of Movement compared with usual Physical and Occupational Therapy on the motor recovery of paretic limbs in patients with a Cerebral Vascular Event.

VARIABLES

Independent Variable

Cerebral vascular event

Conceptual definition. It is defined as a clinical syndrome characterized by the rapid development of signs and/or symptoms usually corresponding to a focal or global neurological condition (applicable to patients with loss of consciousness or acute headache), which persist for more than 24 hours or which lead to death, with no other apparent cause than a vascular origin" ^{1, 2}.

Operational definition. In this work, the patient who comes to request care at the outpatient clinic of the UMFR sXXI will be considered, with the interconsultation format 4-30/8 where it is indicated that the patient suffered a cerebral vascular event and who presents neurological data consistent with the diagnosis, mainly hemiparesis, with or without aphasia. The verification of the diagnosis will be made later in the office, with the support of the computed tomography and verified during the physical examination; It will also be verified that it covers the rest of the selection criteria.

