Indicators. The therapists who will provide the neurorehabilitation programs will always be the same and will handle the same assigned patients, in the same workplace, with common materials, 1-hour sessions, 2 times a week for 6 weeks (12 sessions).

Measurement scale. Qualitative, nominal.

Dependent Variable

Hemiplegia-Hemiparesis secondary to a Cerebral Vascular Event

Conceptual definition. It is the loss of voluntary movement with alteration of muscle tone and sometimes sensation in the entire extension of one side of the body, it can be secondary to injuries, such as the cerebral vascular event that occurs in one hemisphere and affects the extremities and contralateral facial muscles. It behaves like an upper motor neuron syndrome with hypertonia, spasticity or rigidity².

Operational definition. In this work, the motor or sensorimotor disorder of the hemibody secondary to a cerebral vascular event will be verified clinically and by imaging. The usual way of evaluating the hemibody is through internationally accepted functional scales, widely validated in Spanish. For muscle tone, strength, and movement, the Ashworth and Brunnstrom scales will be used. The modified Ashworth scale allows an assessment that, although subjective, is accepted as allowing a quantitative approach. It assesses resistance to passive movement, is easy to apply, works for any joint, and has a high inter-observer reliability rate; grades muscle tone in relation to the range of motion of a joint. The Brunnstrom scale is a facilitation method that uses certain synergistic patterns of the hemiplegic patient to create movements. In this way, it seeks the immediate achievement of more coordinated and normal voluntary primitive movements, enhancing fine motor skills.

Indicators.

Modified Ashworth scale for the measurement of limb muscle tone.

Degree	
0	No increase in muscle tone
1-	Slight increase in tone manifested by minimal resistance at the end of the range of motion during a flexion or extension movement
1+	Slight increase in tone manifested by resistance in less than half the arc of movement
2	Increased pitch by more than half the range of motion, but the joint moves easily
3	Considerable increase in muscle tone with significant difficulty in joint movement
4	Stiffness in flexion or extension

Brunnstrom scale

Degree	
I	Hypotonia. There are no movements.
II	Beginning of recovery. Beginning of basic synergies, mainly through associated reactions. The hypertonia begins.

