Communication is made entirely from incomplete expressions. It requires inference, questions and guessing by the listener. The flow of information can be exchanged, it is limited and the weight of the conversation falls on the listener.	1
The patient can, with the help of the examiner, have a conversation on familiar topics. There is frequent failure to express an idea, but the patient shares the weight of the conversation with the examiner.	2
The patient can deal with virtually all problems of daily living, with little or no help. However, reduced speech and/or comprehension make conversation on certain types of topics extremely difficult or impossible.	3
There is some obvious loss of speech fluency or ease of understanding with no significant limitation of the ideas delivered to their mode of expression.	4
Minimal observable impairments in speech. The patient may present subjective difficulties that are not evident to the listener.	5

Measurement scale. Quantitative, ordinal.

Patient satisfaction when performing rehabilitation therapy

Conceptual definition. Feeling of well-being or pleasure that one has when a desire has been fulfilled or a need covered. In relation to therapy, this feeling is linked to the development of different therapeutic activities ⁵⁰.

Operational definition. For this research, the Intrinsic Motivation Inventory will be used, which is a multidimensional measurement device designed to evaluate the subjective experience of the participants related to an objective activity in experiments; It consists of a varied number of subscale items, all of which have been shown to be factor analytically consistent and stable across a variety of tasks, conditions, and settings. The general criteria for the inclusion of items in the subscales have been a factor loading of at least 0.6 in the appropriate subscale. The multiple investigations in which they are used suggest that the order effects of item presentation appear to be negligible, and the inclusion or exclusion of specific subscales appears to have no impact on the others. Therefore, it is used as the equivalent of satisfaction, pleasure in carrying out the activity, and potential adherence to treatment. The Task Assessment version will be used, the subscales it includes are:

- Interest and satisfaction with the treatment
- Perception of competence (of the patient versus the treatment)
- Effort and importance of treatment
- Stress or tension (caused by the treatment)

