1. Patients who develop dementia or neurological-psychomotor complications during the study.
2. Patients who present a new cerebrovascular event during the investigation
3. Patients who do not complete at least 90% of the program
4. Patients in whom a lack of family support or secondary gain is detected.

STUDY TYPE AND DESIGN

Type study

Clinic

Design Study

Controlled clinical trial, randomized, single-blind.

MATERIAL AND METHODS

Population

Adult patients with a clinically and tomography-confirmed diagnosis of a Cerebral Vascular Event, with body hemiparesis, with or without aphasia.

Geographic scope

Outpatient services and physical/occupational therapy of the Physical Medicine and Rehabilitation Unit XXI Century (PMRUcXXI). Southern Delegation of the Federal District, IMSS.

Limits in time

March 2020 to June 2024.

Study General description

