After working on this task for a while, I felt quite competent.									
Effort and importance of treatment									
I felt it was my choice to do the task.									
I didn't really have the option to do task (R).									
I felt like I was doing what I wanted to do while working on the assignment.									
I felt that I had obligation to do task (R)									
I did the homework because I had no other option (R).									
Stress or strain (caused by treatment)									
I didn't feel nervous about doing task (R).									
I felt tense while doing task.									
I felt relaxed while doing task (R).									
I was anxious while doing task.									
I felt stressed while doing task.									

Ini. Val.: initial valoration; Intermed. Val.: intermediate valoration; Fin. Val.: final valoration.

Subscale scores can be used as dependent variables, predictors, or mediators, depending on the research questions being addressed. The higher the score, the higher the satisfaction.

3. Therapy programs.

- a. Virtual reality program. The activities indicated in the tennis and ski software for the upper limb, covering cracks for both limbs and Star Wars-battles in the galaxy for the hand and fine pincer,

which will be carried out with the interface of the virtual reality equipment "connected" to the patient through movement sensors, with the multiperceptual feedback of the Kinect equipment or with googles.

b. *Movement restriction and induction therapy.* The patient will be placed a sling on the "healthy" thoracic limb, attached to the thorax, through a bra, gently but firmly, in such a way that it does not alter circulation or compress peripheral nerves. It will be explained to you that you should do all your activities with the "sick" member, to the extent possible. The restriction of the healthy side forces the patient to put all his effort into carrying out the activities of daily life, simulated during the therapy. This restriction will be carried out for 1 hour in therapy in the medical unit. And the patient will be told to repeat it at home at least once a day for one to five hours, without receiving support from family members while wearing the sling.

c. *Regular physical and occupational therapy.* The specific activities are shown in Annex 1. They include:

- **Motor management:** tasks to promote mobility of the shoulder, elbow, pentadigital clamp, fine clamp, transfers; volitional movements, eye-motor coordination, hip, knee, ankle and gait mobility.

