- **Sensory training:** deep sensitivity, stereognosis, sensory discrimination, graphesthesia, topognosis and proprioception.

4. *Concentration and analysis of information.* The results of the different evaluations will be noted on the information capture sheet (Annex 2 and 4); Subsequently, they will be entered into an Excel spreadsheet and finally exported for analysis to the SPSS V-19 program.

STATISTICAL ASPECTS

Sampling

Non-probabilistic, of consecutive cases.

Sample size

The sample size calculation was performed to test the working hypothesis* (average difference of 38.6 points and a SD 12.23), with a standardized effect size greater than 1 in a prefabricated table to establish mean differences (Appendix 1. 13 -A)⁵², considering a unilateral hypothesis, in a finite population and without replacement, with a value $\alpha = 0.05$ and $\beta = 0.10$.

For 17 patients plus 20% of possible losses, for a total of 19 patients per group.

* The score of the motor evolution evaluated with the Fugl-Meyer scale was considered, with therapy supported by virtual reality, found in the study of the unit, considered as a pilot^{47, 48}.

Statistic analysis

Descriptive statistics will be carried out for the qualitative variables through tables, graphs and percentages; for the quantitative ones, measures of central tendency and its corresponding dispersion will be used, depending on the distribution of the data. The distribution of the numerical data will be compared with the distribution curve using the Shapiro-Wilk test, depending on the result, the ANOVA or Friedman test will be used for intragroup comparison; for comparison between groups, ANOVA of repeated measures or the Kruskal-Wallis test will be used. In case of detecting variables that could be potentially related to the result, correlation tests such as Pearson or Spearman will be applied. An α value of 0.05 will be considered.

ETHICAL ASPECTS

This research respects the institutional, national and international standards that govern research on human beings in our country. Including the General Health Law, TITLE FIVE Research for Health, sole chapter ⁵³; the regulation of the General Law of Health in Matters of Research for Health ⁵⁴; and the Official Mexican Standard NOM-012-SSA3-2012, which establishes the criteria for the execution of research projects for health in human beings ⁵⁵.

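### Secondary question 3 relates satisfaction to adherence, but the plan has no separate adherence measure, and its 90% completion rule would leave only 11 or 12 clinic sessions among retained patients

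*Combined protocol and SAP*

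**What the plan says.** The protocol lists three secondary questions, in the summary and again under Research Question. The third is "To relate the level of patient satisfaction with adherence to treatment".

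The Variables section has an entry for satisfaction but none for adherence. The satisfaction entry names the Intrinsic Motivation Inventory as the instrument and adds: "Therefore, it is used as the equivalent of satisfaction, pleasure in carrying out the activity, and potential adherence to treatment". The inventory is given at the start, after session 6 and after session 12.

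The only completion rule is elimination criterion 3, which removes "Patients who do not complete at least 90% of the program". The therapy is described as one-hour sessions twice a week for six weeks. The constraint arm also has a home component: "And the patient will be told to repeat it at home at least once a day for one to five hours". No log of it is described.

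The score sheets in Annex 2 and the collection sheet in Annex 4 have no place for sessions attended or home practice. The Statistic analysis section names no analysis of satisfaction against adherence. It says only that, where variables potentially related to the result are detected, "correlation tests such as Pearson or Spearman will be applied".

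**The concern.** An association needs two measured quantities, and here only satisfaction is measured. The one statement on how adherence might be captured points back to the satisfaction inventory, so a high satisfaction score could be reported as if it were evidence of adherence.

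Attendance is the obvious substitute, but it is not collected as data, and the elimination rule removes the patients who attend least. Those patients carry most of the information on whether dissatisfied people stop coming.

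Better adherence is part of the background case for virtual reality. The Transcendence section also makes a benefit conditional on adherence being verified, although that passage concerns equipment in private homes, which clinic attendance would not establish. At stake is one stated secondary objective. The Fugl-Meyer comparison is not affected.

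**Working it through.** **1. What the plan measures.** Satisfaction: the inventory, at three time points. Adherence: no variable, no field in Annex 2 or Annex 4, no named analysis. The only link is the remark that the inventory also stands for potential adherence.

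**2. What the 90% rule leaves.** Inputs: two sessions a week and six weeks (Variables section), 90% (elimination criterion 3).

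- Sessions: 2 × 6 = 12, which reproduces the plan's figure.
- Threshold: 0.90 × 12 = 10.8.
- 10/12 = 83.3%, eliminated; 11/12 = 91.7% and 12/12 = 100%, retained.

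On this reading retained patients can take two attendance values, 11 or 12.

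**3. What the restriction could cost.** The documents give no attendance distribution, so these inputs are assumptions: per-session attendance logit-normal between patients with SD 1, median 0.90 to 0.98; correlation ρ of 0.3 or 0.5 between satisfaction and the tendency to attend; sessions binomial out of 12; one million simulated patients per row. Loss is 1 − (r retained / r all), computed before rounding.

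| Median attendance | Eliminated | ρ | r, all | r, 11–12 only | Loss |
|---|---|---|---|---|---|
| 0.98 | 7% | 0.3 | 0.14 | 0.09 | 35% |
| 0.98 | 7% | 0.5 | 0.24 | 0.16 | 35% |
| 0.97 | 12% | 0.3 | 0.16 | 0.10 | 41% |
| 0.97 | 12% | 0.5 | 0.27 | 0.16 | 40% |
| 0.95 | 21% | 0.3 | 0.19 | 0.09 | 50% |
| 0.95 | 21% | 0.5 | 0.31 | 0.16 | 49% |
| 0.90 | 41% | 0.3 | 0.21 | 0.08 | 61% |
| 0.90 | 41% | 0.5 | 0.35 | 0.15 | 59% |

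With SD 0.7 or 1.5, settings that eliminate 7–22% of patients also fall within about 35–50%.

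For scale, the Sample size section states: "For 17 patients plus 20% of possible losses, for a total of 19 patients per group". Going from 17 to 19 actually covers 2/19 = 10.5% losses; 20% would need 17 × 1.2 = 20.4 or 17 / 0.8 = 21.25 per group. Either loss figure sits in the 7–22% band.

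**4. What the trial could detect.** Patients: 3 × 17 = 51 to 3 × 19 = 57. Two-sided 0.05 and 80% power, by Fisher's z: r = tanh[(1.960 + 0.842) / √(n − 3)].

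- n = 51: tanh(2.802 / 6.928) = 0.38.
- n = 57: tanh(2.802 / 7.348) = 0.36.

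**The case against.** The inventory is offered only as a proxy for potential adherence. Nothing says it is the adherence measure for question 3, and the procedures allow its subscales to serve in different roles. A reader might infer that the plan correlates a score with itself. The documents do not go that far: circularity is one reading of an under-specified objective. What stands is that no other adherence measure is offered.

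Someone must count sessions to apply the 90% rule, so attendance could probably be recovered. The criteria also do not say that eliminated patients leave every analysis. Both points are fair. Exclusion is the natural reading of elimination but remains an inference, and the plan provides neither an analysis set that keeps these patients nor a field for their attendance.

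The program might include home practice, in which case the two-value count would not follow for the constraint arm. The documents do not settle this. Home practice is described for one arm only and is not recorded, so as planned it cannot supply a measure comparable across arms.

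The attenuation figures rest on an assumed model. They do, and they should be read as a range. The 11-or-12 count does not depend on them.

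**Conclusion.** The point holds as a failure to operationalise a stated secondary objective, made worse by a rule that removes the patients it needs. It rests on two readings: that the program means the 12 clinic sessions, and that eliminated patients are left out of the analysis. Under the assumed model the correlation is weakened by roughly 35–50% when about 7–22% of patients are eliminated, and by more if more are eliminated.

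Three stronger conclusions might be inferred and are not supported. The question is not unanswerable in principle, since a small change repairs it. The correlation among retained patients need not be near zero: it is about 0.08–0.16 in the table. A loss well above half requires about 40% of patients to be eliminated, far more than the plan allows for.

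This should be corrected, but it does not bear on the primary comparison.

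**What to change.** - In the satisfaction entry of the Variables section, delete the words that make the inventory stand for potential adherence.
- Define adherence for this objective as supervised sessions attended out of 12, and add one attendance line to Annex 4.
- For this objective only, analyse every randomised patient with an inventory score, including those below 90%, with therapy group taken into account. Name in advance which inventory assessment supplies the score.
- As a supporting analysis that puts satisfaction before adherence, relate the session-6 inventory to attendance at sessions 7–12. Report how many patients stopped before session 6, since this analysis cannot include them.
- Report an estimate with a confidence interval. Most of the full-sample correlations in the table lie below the detectable 0.36–0.38, so a non-significant result would say little.
- State whether the constraint arm's home practice counts towards the 90%. Keep it out of this adherence measure, because it is unrecorded and not comparable across arms.

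The cost is one line on a form and a few sentences of protocol text. No visit, treatment or primary analysis changes. The downside is that attendance is a coarse measure, coarser still over six sessions, and power stays low.
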